Project Title: Iterative Beta Testing of Videos for the DIPPer Academy

NCT Number: NCT03385265

Date: 9/27/2021

The incidence of type 1 diabetes mellitus (T1D) is increasing in young children (<6 years old).¹⁻⁴ Yet, the development of age-targeted behavioral interventions for this vulnerable patient group has been limited. Young children will face a lifetime with T1D, substantially increasing their overall risk for micro- and macrovascular complications.^{5, 6} In addition, young children have a higher risk of cognitive deficits than children diagnosed at an older age,⁷⁻¹⁰ suggesting the potential for greater impairment in education and job opportunities. Establishing good glycemic control early in the course of T1D can reduce the risk for complications (viz., metabolic memory),¹¹⁻¹³ thereby underscoring the importance of intervening with young children who are likely to benefit from the risk reduction into adolescence.^{5, 6, 11, 14}

Unfortunately, research shows that many young children with T1D exhibit blood glucose levels that exceed the current U.S. and international targets.¹⁵ They also can experience problems with high "glycemic variability,"^{16, 17} and hypoglycemia.^{5, 16-18} Within families, the research shows challenges parents face in managing their child's T1D including moderate to high rates of parenting stress and hypoglycemia fear,¹⁹⁻²¹ disrupted sleep schedules,¹⁸ difficulty in managing their child's disruptive behaviors,^{22, 23} depressive and anxiety symptoms,^{19, 24} and decreased quality of life.²⁴ Caring for a young child with T1D is uniquely challenging often because of the typical and developmentally appropriate behaviors exhibited by young children, who can be unpredictable, idiosyncratic, and contrary.^{5, 25-27} The young child's natural tendency to seek more independence may complicate daily T1D self-care; he or she may refuse to cooperate with insulin injections or pump site changes, glucose checks, or treatment for a low blood glucose level.⁵ Likewise, the tendency among young children to be unpredictable in their eating and activity patterns²⁶ can make it hard for parents to plan meals, administer insulin before meals, and effectively manage glucose levels between meals.^{5, 6}

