Before the project begins, Institutional Review Board approval will be obtained from the Institutional Review Board at CMH. In addition, all research team members will complete certification in topics related to the responsible conduct of research. Certification will involve passing an online competency in each of the following areas: Foundations of Responsible Research Conduct, Safe Handling of Blood Products, Research Administration, and Conflict of Interest.

Minimization of Risks:

1. We will use several procedures to ensure confidentiality of information collected throughout the project. Each participant will be assigned a unique subject ID number which will be used to identify/store all data collected from that participating family. When possible, all identifying information will be physically separate from the remainder of the data. Identifying information will be recorded only for the purpose of matching and merging databases and will be stored in a locked file cabinet or on a secured server separate from any corresponding data. All research data will be stored in a secure, password protected database and archived in a password-protected back up file. We will minimize risks to privacy during data collection by giving parents the option of home visits and using on-line survey completion.
2. During recruitment and the informed consent process, parents will be informed as to the time commitment necessary for participation, as well as the potential risk for emotional/social discomfort. Parents will be informed that they have the right to discontinue participation in the projects at any time. They also have the right to refuse to answer specific questions related to the projects. While the surveys proposed for this study are generally benign in nature and have been used in other pediatric diabetes research projects, should participation in this study unmask or exacerbate parents' feelings about diabetes, members of the research team will be clinically trained to provide a list of resources. Parents may be asked to complete a screener for depressive symptoms. These screeners will be reviewed by the post-doctoral fellow within 24 hours of completion and the results shared with the PI. If a screener suggests a parent may be experiencing symptoms of depression, the PI or fellow (under direct clinical supervision of the PI) will contact the parent to review the results and to provide a list of resources to the parent.

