Hypothesis 4: DIPPer Academy will result in greater reported Time 2 parent self-efficacy and lower reported post-treatment parenting stress, mealtime behavior problems and hypoglycemia fear than standard of care, controlling for Time 1 measurements on these variables.

Data Analyses. For the primary outcomes, we will conduct a sensitivity analysis to test for any effects due to attrition. We will also use an intent-to-treat strategy and imputation model to examine parent data even if they are lost to attrition. For all analyses, we will include parental depression as a covariate if determined to be correlated with our outcome variables. To test for between group differences in glycemic levels (Hypothesis 1), we will conduct an ANCOVA with Time 2 (post-treatment) score as the outcome, group (treatment vs. control) as focal predictor, and Time 1 (baseline) score as covariate. In addition, we will calculate within group standardized effect sizes (in SD units) and within-group changes for HbA1c based on Time 1 and Time 2 values. To estimate and test time trends in glycemic levels for DIPPer participants (Hypothesis 2) we will use appropriate generalized mixed models with a random parent intercept to account for clustering of repeated measures within parents. Finally, to test for post-treatment differences between groups in reported parent self-efficacy, parenting stress, mealtime behavior problems, and hypoglycemia fear (Hypothesis 3) we will calculate within group standardized effect sizes (in SD units) and within group changes for parents' PSESDM, PIP, BPFAS, and HFS-PYC scores using parents' Time 1 and Time 2 data. To test for statistical significance, we will conduct an ANOVA for each variable as described above for Hypothesis 1.

REFERENCES

1. Liese, A.D., et al., *The burden of diabetes mellitus among US youth: prevalence estimates from the SEARCH for Diabetes in Youth Study*. Pediatrics, 2006. **118**(4): p. 1510-8.
2. Vehik, K., et al., *Increasing incidence of type 1 diabetes in 0- to 17-year-old Colorado youth*. Diabetes Care, 2007. **30**(3): p. 503-9.
3. Dabelea, D., *The accelerating epidemic of childhood diabetes*. Lancet, 2009. **373**(9680): p. 1999-2000.
4. Patterson, C.C., et al., *Incidence trends for childhood type 1 diabetes in Europe during 1989-2003 and predicted new cases 2005-20: a multicentre prospective registration study*. Lancet, 2009. **373**(9680): p. 2027-33.

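### Does admitting parental depression as a covariate only when it correlates with the outcomes, with no stated cut-off or visit, put the treatment comparison at risk?

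*Combined protocol and SAP*

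**What the plan says.** The Data Analyses paragraph of the SAP sets one rule for depression: "For all analyses, we will include parental depression as a covariate if determined to be correlated with our outcome variables". It does not say how strong the correlation must be, with which outcome and visit it is computed, or in which data. This trial's own data is the natural reading, but it is a reading.

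The same paragraph does fix the visit for the outcome covariate in the Hypothesis 1 ANCOVA: "Time 1 (baseline) score as covariate". No such limit is attached to depression. For Hypothesis 2 the plan says "we will use appropriate generalized mixed models with a random parent intercept to account for clustering of repeated measures within parents". Hypothesis 4 expects higher parent self-efficacy and "lower reported post-treatment parenting stress, mealtime behavior problems and hypoglycemia fear than standard of care".

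The only mention of collecting depression data is in the protocol, under Minimization of Risks, item 2: "Parents may be asked to complete a screener for depressive symptoms". The instrument and visit are not named. The same item gives parents a right to skip questions: "They also have the right to refuse to answer specific questions related to the projects". Surveys run at Times 1, 2 and 3 (Human Subjects Involvement, Characteristics, and Design). On missing data the SAP says: "We will also use an intent-to-treat strategy and imputation model to examine parent data even if they are lost to attrition".

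**The concern.** A covariate that enters only when it correlates with the outcome makes the fitted model depend on the outcome data. With no cut-off written down, an analyst could fit the model both ways and keep the better result.

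The open visit looks worse. Two of the three survey visits come after randomisation. The background lists "depressive and anxiety symptoms" beside parenting stress and hypoglycemia fear among parents' difficulties, and Hypothesis 4 expects the last two to fall. If the intervention also lowered depression, adjusting for a Time 2 depression score would remove part of a real effect. If the outcome did not change, it would create a difference that is not there. The rule covers every analysis, including HbA1c under Hypothesis 1, in a trial of at most 50 parents.

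**Working it through.** **Inputs.** The documents give no alpha, effect size, SD, correlation, cut-off or allocation ratio, so there is no planned figure to reproduce. From the documents: at most 50 parents, and an ANCOVA of Time 2 on group and Time 1. Assumed: 25 per arm, two-sided 5% test, within-arm SD 1, Time 1-Time 2 correlation 0.6 for the outcome and for depression, same-visit depression-outcome correlation r = 0.2, 0.3 or 0.4, Time 1 outcome with Time 2 depression 0.6r, and a true effect of 0 or 0.50 SD. The correlation of Time 1 depression with the Time 2 outcome is set to r (setting A) or 0.6r (setting B).

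**Step 1: how often depression enters.** With a p<0.05 screen the cut-off is |r| = t/√(n−2+t²) = 2.011/√(48+4.04) = 0.279. The share of null trials that admit depression is in the table. It varies widely, which shows that the model is unpredictable, not that the inference is wrong.

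**Step 2: the rule applied mechanically with a Time 1 score.** Type I error uses 40,000 trials per setting; power at 0.50 SD uses 20,000.

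| Setting, r | Admitted | Type I error, conditional | Power: left out | Power: always in | Power: conditional |
|---|---|---|---|---|---|
| A, 0.2 | 28.6% | 5.1% | 57.3% | 56.9% | 57.0% |
| A, 0.3 | 57.3% | 5.2% | 57.4% | 57.5% | 57.6% |
| A, 0.4 | 83.6% | 5.0% | 57.7% | 58.7% | 58.6% |
| B, 0.2 | 13.1% | 5.0% | 56.9% | 56.1% | 56.6% |
| B, 0.3 | 24.0% | 4.9% | 57.2% | 56.3% | 56.8% |
| B, 0.4 | 39.2% | 5.0% | 56.8% | 55.9% | 56.5% |

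Monte Carlo error on power is about 1.96 × √(0.57 × 0.43/20,000) = 0.7 points. The mean estimate under the conditional rule is 0.496-0.499 against a true 0.50.

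**Step 3: does this depend on the assumed structure?** For power it does. In A and B the Time 1 outcome already carries most of what depression could add. Suppose instead that Time 1 depression is unrelated to the Time 1 outcome and correlates 0, 0.3 or 0.5 with the Time 2 outcome:

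| Correlation with Time 2 outcome | Left out | Conditional (p<0.05) | Always in |
|---|---|---|---|
| 0 | 57.3% | 57.2% | 56.5% |
| 0.3 | 57.3% | 60.2% | 62.7% |
| 0.5 | 56.9% | 76.4% | 77.2% |

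Type I error under the conditional rule stays at 5.0-5.1%, and the estimate at 0.49-0.50. The rule costs at most about 2.5 points against always adjusting (62.7 − 60.2) and gains on leaving depression out when it is informative. Always adjusting for an uninformative score costs √(46/45) = 1.011, about 1.1% in the standard error.

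**Step 4: an analyst who reports the best of several models.** In A and B, the best of two models (none, Time 1) gives type I error of 5.4-6.1%. The best of three (none, Time 1, Time 2) gives 6.2-7.2%. Under Step 3's structure, with 40 or 50 parents, the best of two gives 5.6-8.2%.

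**Step 5: a Time 2 score in the model.** Given the Time 1 outcome, the coefficient on Time 2 depression is (r − 0.6 × 0.6r)/(1 − (0.6r)²) = 0.64r/(1 − 0.36r²). If treatment lowers depression by an assumed 0.3 SD, the estimate moves by 0.3 times that:

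- r = 0.2: 0.3 × 0.128/0.9856 = 0.039, so 0.50 becomes 0.461
- r = 0.3: 0.3 × 0.192/0.9676 = 0.060, so 0.50 becomes 0.440
- r = 0.4: 0.3 × 0.256/0.9424 = 0.081, so 0.50 becomes 0.419

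Simulated power falls to about 50%, 48% and 46%. With no true effect the same shift of 0.04-0.08 SD appears, against the intervention. If depression does not change, there is no shift.

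**Step 6: Hypothesis 2.** A Time 1 main effect does not alter the time slope with complete data. With 15% of follow-up visits missing, the slope changes by 0.004 on average, against a standard error of 0.094 (25 parents, three visits, r = 0.4).

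**The case for a change.** The strongest case for a change is that the authors knew how to fix a visit, did so for the outcome covariates, and did not for depression. A Time 2 score would therefore comply with the text, and stronger assumptions make it look worse. With a correlation of 0.5, a 0.3-0.5 SD fall in depression and no true effect on the outcome, type I error under a p<0.05 screen reaches 12.5-24.9%; at a correlation of 0.3 it is 6.0-7.8%. With a true 0.50 SD effect, across both correlations, the estimate falls to between 0.43 and 0.25 SD and power to 27-48%. One sentence would close the gap.

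The detail is indeed missing, and the algebra of post-randomisation adjustment is right. But the harm needs an analyst to choose a score that nothing in the plan asks for, when the covariate beside it is a baseline one, and also needs a fall in depression that no stated hypothesis predicts. The null shift runs against the intervention when lower depression goes with better outcomes, so it would not manufacture a benefit. Best-of-several reporting departs from the written rule, which turns on correlation with the outcome and not on the treatment p-value.

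Fixing the choice in advance also buys little. Because the screener is optional, any such wording still depends on whether every parent receives it. Leaving depression out altogether would give up power wherever the score is informative (Step 3).

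**Conclusion.** No change to the plan follows. On the natural reading, a Time 1 score and a cut-off that is kept to, type I error stays at about 5% and the estimate is essentially unbiased. Power is within about one point of always or never adjusting under settings A and B. Where depression adds information beyond the Time 1 outcome, power is at most about 2.5 points below always adjusting and above leaving it out. Whether depression is informative cannot be known from the documents.

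The one reading that distorts the result, a post-randomisation score, is neither excluded nor called for. Its size, 0.04-0.08 SD, rests on an assumed 0.3 SD fall in depression and correlations of 0.2-0.4; the stronger assumptions above give more. In a pilot with no stated alpha or power target, this is a gap that a competent analyst fills in the usual way: use the Time 1 score, settle the criterion before looking at treatment results, and let the planned imputation cover skipped or missing screeners. A clarifying line to that effect would do no harm, but the conclusions do not depend on it.

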Human Subjects Involvement, Characteristics, and Design

Aim 3 will involve a randomized pilot test (RPT) of DIPPer Academy. We propose to enroll up to 50 parents of young children with T1D into the RPT. Parents who participate will be randomized to either an immediate treatment or a control group. Parent will be recruited via letter, telephone call, or in clinic. Parents will be asked to give written informed consent for their participation and permission to obtain a measure of HbA1c level in their child. Parents will be asked to complete study assessments (online surveys) at Time 1 (baseline), Time 2 (post-treatment), and Time 3 (follow up). We will collect child HbA1c at Times 1, 2, and 3. We anticipate that parents may spend about 3 hours completing the DIPPer Academy curricula spread out across 14 weeks of treatment. We expect the surveys at Times 1, 2, and 3 will each time take about 20 minutes to complete.

All parents regardless of gender, race, ethnicity, and socioeconomic class will be considered potentially eligible to participate. Specific inclusion criteria for parents are:

1. Parents of a young child who is between 3-5 years old and at least 3 months post T1D diagnosis.
2. Parents who are English-speaking.

Parent exclusion criteria for are:

1. Young children with evidence of type 2 diabetes or monogenic diabetes.
2. Parents with evidence of severe psychiatric disorder.
3. Young children with a comorbid chronic illness (e.g., renal disease) that requires ongoing care beyond T1D.
4. Young children with a history of anemia or medication use that may interact with glycemic control (e.g., systemic steroids).
5. Young children with an HbA1c $\leq 7.5\%$ (which is the current ADA target).⁶

Sources of Materials

For all participating parents, we will collect demographic data and medical history data specific to T1D. We will also collect data via parent surveys and usage data collected during the intervention (i.e., website use statistics). Survey and parent usage data will be entered and stored in an electronic database (REDCap). This database will be located on a secured server maintained by the Department of Biostatistics at KUMC. No one outside of the research team will have access to data identifying the families who participated. We will obtain a measure of child HbA1c.

Potential Risks

The overall risks of participation in this project are no more than minimal.

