1. Because the research requires the collection of personally identifying data, there is always a risk of breach of confidentiality.

2. Parents will be requested to disclose information about their child's diabetes adherence and about their values, sources of motivation, regimen knowledge, their psychosocial and behavioral functioning, their priorities for diabetes management, and their concerns about their child. Disclosing this information may potentially lead to emotional discomfort. Parents may also feel inconvenienced by the amount of time required to complete the study.
3. We will obtain a measure of children's HbA1c levels.
4. There is the potential risk that parents participating in the projects will find their participation time-consuming and inconvenient.

ADEQUACY OF PROTECTION AGAINST RISKS

Recruitment and Informed Consent

Potential subjects will be identified by a review of the clinic database and in consultation with the clinic director at CMH. Eligible parents will be notified of the project by a letter sent by the study team, by a telephone call placed by a member of the study team, or by in person solicitation. All parents will be explicitly told that they can continue to receive the same high quality of care from their child's diabetes team regardless of their decision to participate in the research projects. During the initial study contact, a member of the research team will describe the study and parents will have a chance to ask questions. During the informed consent process, parents will be explicitly told that their participation is voluntary and that they maintain the right to discontinue participation at any time. The research protocol and consent documents will be approved by the Institutional Review Board at CMH. (Note, KUMC and CMH already have an agreement in place which will allow the PI to seek a Request to Rely so that CMH will be the IRB of record for both CMH and KUMC should the project proceed). Consent forms will be filed in a confidential research file and copies will be given to parents/guardians. The consent forms will include contact information for the Principal Investigator and Co-Investigators should families have any questions or concerns regarding the research project. No study procedures will occur before written consent is obtained from parents.

Protection Against Risk

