3. We propose to collect children's HbA1c levels at Times 1, 2, and 3 during the randomized pilot trial. The purpose of measuring children's HbA1c levels will be to explore the impact of DIPPer Academy on children's glycemic control even though children will not participate in the intervention.
4. Participating may inconvenience parents. We will minimize the potential risk of inconvenience by offering parents the opportunity to participate in a project from their home. If parents do not own a mobile device or would prefer not to use their personal mobile device to access DIPPer Academy, we will loan parents an iPad Mini with data plan for use during the study. Prior to informed consent, parents will be informed

of their ability to discontinue participation in a research project at any time without penalty. Discontinuation from a research project will not impact a child's care by their Diabetes Team. The PI will ensure that research staff is trained to explicitly inform parents of the purpose, procedures, and risk related to participating in one of these research projects.

5. We hypothesize that DIPPer Academy will be deemed feasible and acceptable by parents and will have a beneficial effect on children's HbA1c. We have attempted to minimize the potential risk of inconvenience to parents participating in DIPPer Academy by designing the intervention as a mHealth intervention. Parents will be able to access the DIPPer Academy website from their computer or any mobile device. From the website, they will be able to view the video microlectures at any time and as often as they wish.
6. [name] will be available to provide medical supervision.

POTENTIAL BENEFITS OF THE PROPOSED RESEARCH TO THE SUBJECTS AND OTHERS

There is a chance parentss will perceive no direct benefit to study participation. In this case, parents who elect to participate have the opportunity to contribute to our evolving knowledge related to glycemic control in children with T1D and the development of preventative interventions to promote optimal glycemic control in young children with T1D.

IMPORTANCE OF THE KNOWLEDGE TO BE GAINED

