Before the proposed projects begin, we will obtain approval from the Institutional Review Board (IRB) at Children's Mercy Hospital (CMH). The PI will also secure approval from her home institution, the University of Kansas Medical Center, to Rely on the IRB at CMH as the IRB of record for the projects. In compliance with regulatory practices, the PI and Co-Investigators will secure "continuing approval" for the research projects each year from the CMH IRB and will notify the CMH and KUMC IRB's if any Adverse Events (AEs), Other Reportable Information and Occurrences (ORIOs), and Unanticipated Problems Involving Risks to Subjects or Others (UaPs) occur in the conduct of the projects. The PI (with the assistance of Co-Investigators, as needed) will assume primary responsibility for reporting AEs, ORIOs, UaPs, or unforeseen outcomes to the IRBs in a timely fashion and will promptly inform the study sponsor of any action taken by the IRB at CMH because of continuing review. The proposed research designs have been developed keeping in mind how to maximize specific data collection and minimize risk to parents (i.e., psychometrically sound and benign questionnaires, [name] availability to provide medical supervision of patients). However, at the discretion of the CMH IRB, the PI will recruit a Data Safety and Monitoring Board (DSMB) to oversee and monitor the data collection and intervention delivery. We propose members of the DSMB will include an endocrinologist, a psychologist, and a certified diabetes educator. If a DSMB is requested by the CMH IRB, we propose that the DSMB will meet at least annually by teleconference. For each of these meetings, the PI and the biostatistician will jointly prepare a summary of the following topics:

Performance monitoring: A report of subject recruitment/retention, protocol adherence, and quality of data collection procedures.

Safety monitoring: A review of safety of the participants, including confidentiality and any adverse events or side effects related to the study procedures.

STATISTICAL ANALYSIS PLAN

Hypotheses:

Hypothesis 1: DIPPer Academy will result in better Time 2 HbA1c than standard of care controlling for Time 1 measurements.

Hypothesis 2: DIPPer Academy will result in improvements in HbA1c across time (a decreasing time trend for HbA1c).

Hypothesis 3:

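### The Hypothesis 2 HbA1c trend is tested in the DIPPer arm alone, so it cannot be attributed to DIPPer Academy, and no between-arm HbA1c analysis reaches Time 3

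*Combined protocol and SAP*

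**What the plan says.** The design section sets up a randomized comparison: "Parents who participate will be randomized to either an immediate treatment or a control group". HbA1c is scheduled for everyone at three visits: "We will collect child HbA1c at Times 1, 2, and 3". Under Minimization of Risks, item 3, the reason given is this: "The purpose of measuring children's HbA1c levels will be to explore the impact of DIPPer Academy on children's glycemic control".

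The Statistical Analysis Plan then states two HbA1c hypotheses:

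- "Hypothesis 1: DIPPer Academy will result in better Time 2 HbA1c than standard of care controlling for Time 1 measurements". Under Data Analyses this becomes an ANCOVA of Time 2 HbA1c, with group as the focal predictor and Time 1 as covariate.
- "Hypothesis 2: DIPPer Academy will result in improvements in HbA1c across time (a decreasing time trend for HbA1c"). The matching analysis reads: "To estimate and test time trends in glycemic levels for DIPPer participants (Hypothesis 2) we will use appropriate generalized mixed models", with a random intercept per parent. No group term, group-by-time term or comparator is mentioned.

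The only other HbA1c output is a set of within-group effect sizes and changes, which use Times 1 and 2. The text of Hypothesis 3 is absent from the list, possibly through removal. The Data Analyses paragraph attaches that number to the parent-reported outcomes and contains no Time 3 between-arm HbA1c analysis.

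**The concern.** Hypothesis 2 makes a causal claim, but its test has no control. A slope in one arm is the sum of the intervention effect and everything else that moves HbA1c over the same months: routine clinic care, season, and being in a study. The one-arm model cannot separate them. A shared fall would be credited to DIPPer Academy, and a shared rise could conceal a real benefit.

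The gap is specific. At Time 2 the Hypothesis 1 ANCOVA gives a proper randomized answer. What lacks one is the trend itself and Time 3, so any statement that an HbA1c difference lasts to follow-up would rest on an uncontrolled trend. The protocol's own background faults earlier work in this population for lacking randomization, and this analysis brings that weakness back inside a randomized trial.

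A second mechanism may add to the first. The exclusion list removes "Young children with an HbA1c" at or below 7.5%. If the value that qualifies a child is also the Time 1 value, later values will on average be lower through regression to the mean. The documents do not say whether it is. The recruitment section points to an earlier clinic value: "Potential subjects will be identified by a review of the clinic database and in consultation with the clinic director at CMH".

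**Working it through.** **No figure to reproduce.** The documents give no alpha, power, SD, correlation, effect size or dropout rate for HbA1c. The only input they supply is a maximum of 50 parents in total. Everything else below is assumed: 1:1 allocation (25 per arm), SD 1.0 to 1.2 HbA1c points, correlation 0.7 between visits, three equally spaced visits, a linear slope, and a two-sided 5% test (2.5% in the downward direction).

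**Standard errors.** Code the visits -1, 0, 1. In a balanced random-intercept model the residual variance is SD² × (1 - r), and the squared time codes sum to 2 per child.

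- One arm: SE = √[SD² (1 - r) / (2n)]. With SD 1.0 and n = 25, √(0.30 / 50) = 0.077. With SD 1.2, √(0.432 / 50) = 0.093.
- Difference between two equal arms: √2 = 1.41 times as large, that is 0.110 and 0.131.

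A total change D from Time 1 to Time 3 is a slope of D/2 per visit. The noncentrality is (D/2)/SE, with 2n - 1 = 49 degrees of freedom for one arm and 4n - 2 = 98 for the contrast.

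**Shared drift, zero treatment effect.** For SD 1.0 and D = -0.3 the noncentrality is -0.15 / 0.0775 = -1.94, which gives a significant decrease in 47.5% of trials. The simulated results (40,000 trials per setting) agree with this formula within rounding and simulation error:

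| Total drift | SD | One arm, n = 25 | One arm, n = 20 | Between-arm slope |
|---|---|---|---|---|
| -0.2 | 1.0 | 24.4% | 19.9% | 2.4–2.7% |
| -0.3 | 1.0 | 47.5% | 39.2% | 2.4–2.7% |
| -0.2 | 1.2 | 18.4% | 15.4% | 2.4–2.7% |
| -0.3 | 1.2 | 35.5% | 28.8% | 2.4–2.7% |

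The between-arm column stays near 2.5% because a shared drift cancels. The Hypothesis 1 ANCOVA at Time 2 also stays at 2.4% to 2.7%.

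**Masking, true effect of -0.5 points by Time 3, 25 per arm.**

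| Shared drift | SD 1.0, one arm | SD 1.2, one arm |
|---|---|---|
| none | 88.5% | 74.9% |
| +0.2 | 47.7% | 35.3% |
| +0.3 | 24.2% | 18.0% |

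The between-arm contrast stays at about 62% (SD 1.0) and 47% (SD 1.2) throughout. The two tables are not independent evidence: -0.5 + 0.2 = -0.3 and -0.5 + 0.3 = -0.2, so the one-arm test sees the same net slopes as in the first table.

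**Regression to the mean, no drift and no effect.** If Time 1 is the qualifying value, the expected fall is (1 - r) × SD × φ(a) / [1 - Φ(a)], with a = (7.5 - mean)/SD. For a clinic mean of 8.0, SD 1.0 and r = 0.5, a = -0.5, the ratio is 0.509, and the fall is 0.5 × 1.0 × 0.509 = 0.25 points. Over means of 8.0 to 8.5, SD 1.0 to 1.2 and r from 0.5 to 0.9, the simulated fall is 0.04 to 0.26 points, and the one-arm test declares a false decrease in 6% to 24% of trials. A wider grid of means (8.0 to 8.8) and SDs (1.0 to 1.3), with r from 0.5 to 0.8, gives 5% to 30%. If a separate earlier value decides entry and all visits are equally correlated, the rate is 2% to 3%, which is nominal. In the first grid the two-arm tests stay near 5% two-sided in every case.

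**The case against.** The best reply is that the analysis fits the hypothesis. Hypothesis 2 names no comparator and defines itself as a decreasing trend; the between-arm question belongs to Hypothesis 1. The within-group changes from Time 1 to Time 2 would also show the control arm's movement beside the DIPPer trend, so shared drift up to Time 2 would be visible. Replacing the trend with a contrast costs power in a small trial. If controls are on a waiting list, there may be no clean Time 3 contrast at all. Finally, this is a pilot in which HbA1c is exploratory, and every drift figure is assumed.

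Much of this limits the point without removing it. The stakes are low: no alpha, power or decision rule hangs on Hypothesis 2. The figures are illustrations, and the regression-to-the-mean figure applies only if Time 1 is the qualifying value. The crossover question is open and must be settled before a Time 3 contrast is promised.

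Two things remain. The hypothesis attributes the trend to the intervention, and the test cannot support that. The within-group summaries leave the Hypothesis 2 test unchanged and, like the ANCOVA, say nothing about Time 3. The higher one-arm power is a fair comparison only if there is no shared drift, which is exactly what a one-arm analysis cannot check.

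**Conclusion.** The concern holds. The one-arm trend cannot support the causal wording of Hypothesis 2, and the plan contains no between-arm HbA1c analysis at Time 3 although HbA1c is collected then. This rests on the text and on none of the assumed values.

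The size does rest on them. A modest shared drift of 0.2 to 0.3 points would raise the chance of a false decrease from 2.5% to 18% to 48% (15% to 39% with 20 completers per arm). In the opposite direction it would cut detection of a 0.5-point benefit from 75% to 89% down to 18% to 48%. The Hypothesis 1 comparison at Time 2 is unaffected. The point should be fixed, but in this pilot the consequence is an over-read or missed signal, not a failed confirmatory test.

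**What to change.** Fit the Hypothesis 2 mixed model to both randomized arms at Times 1, 2 and 3 with group, time and group-by-time terms. Base Hypothesis 2 on the between-arm difference in HbA1c change from Time 1, notably at Time 3, with confidence intervals. Report the DIPPer-only trend as descriptive.

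State whether and when controls receive DIPPer Academy. If they receive it before Time 3, limit the between-arm contrast to the period before that and say that the later trend is uncontrolled. A sentence on whether the qualifying HbA1c may serve as Time 1 would help interpretation, but the change does not depend on it.

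If controls do not cross over before Time 3, the cost is wording in the analysis plan, because the HbA1c measurements are already scheduled. The statistical price is a standard error 1.41 times as large: with no drift and a true effect of -0.5 points, power is 47% to 62% instead of 75% to 89%. If controls do cross over before Time 3, no between-arm Time 3 contrast is available, and the change there is limited to labelling.
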